
Name of Sponsor:	Pierre Fabre Médicament represented by the Institut de Recherche Pierre Fabre (IRPF)
Name of Finished Product:	Encorafenib, Binimetinib, Cetuximab
Test Product, dose and mode of administration:	
Encorafenib: 300 mg PO (oral capsule 4X 75 mg) QD. Binimetinib: 45 mg PO (oral tablet 3X 15 mg) BID. Cetuximab: 400 mg/m² intravenous (IV) at Cycle 1 day 1 then 250 mg/m² IV every week (QW) for the first 28 weeks. Then, 500mg/m² IV every two weeks (Q2W) from week 29 (Cycle 8 day 1).
 
Since implementation of the Urgent Safety Measure (USM) on 26 Mar 2020, to ensure the subjects' safety in the clinical trial by decreasing the number of clinic visits in the context of COVID-19 pandemic, Cetuximab infusions can be given every two weeks at the dose of 500 mg/m² administered as a 120-min IV infusion (i.e. on D1 and D15 of each cycle) regardless of the cycle number, after the investigator has evaluated the benefit/risk ratio for the subject with regards to Covid-19 pandemic.
 
If there is a dose modification prior to switching to the biweekly schedule, the total dose per cycle should be maintained (i.e. 200mg/m² QW may be changed to a 400mg/m² Q2W). Cycle duration: 28 days.

Duration of Treatment:	
The treatment will be administered during Main study and Study extension periods until disease progression, unacceptable toxicity, subject's decision, withdrawal of consent, initiation of subsequent anticancer therapy or death. After discontinuation of study treatment, there will be a 30-day safety follow-up period. Subjects will then enter a survival follow-up period. If a subject discontinues the treatment for a reason other than progressive disease, tumor assessment must be performed (as per local and central review) until the start of new anti-cancer therapy, disease progression, death, lost to follow-up, subject decision or withdrawal consent or until the End of the Study.

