i	Visual assessment (General inspection of the eyes, examination of motility and alignment, visual disturbance including diminished central vision, blurred vision or loss of vision) to be performed on site by the investigator. Full ophthalmic examination by ophthalmologist to be performed at EOT and, if clinically indicated during treatment, including best corrected visual acuity for distance testing, slit lamp examination, intraocular pressure and dilated funduscopy with attention to retinal abnormalities, OCT and/or fluorescein angiography as appropriate. A full ophthalmic examination at the 30-day follow up is only required if there was a clinically significant abnormality noted at EOT.
j	Dermatologic examinations are to be performed every 8 weeks from Cycle 1 Day 1 (i.e., on Day 1 of Cycles 3, 5, 7...).
k	ECHO/MUGA scans are to be performed on Cycle 2 Day 1 and Cycle 5 Day 1, then every 12 weeks and EOT
l	Tumor evaluations are to be performed every 6 weeks (\pm 7 days) from first dose for the first 12 weeks, then every 8 weeks (\pm 7 days) until disease progression. The time window allowed for the first tumor assessment (i.e. day 42 from first dose) is +7 days.
m	If a subject discontinues study treatment for reasons other than disease progression, then tumor assessments must be performed (as per local and central review) every 6 weeks (first 12 weeks) then every 8 weeks until the start of new anti-cancer therapy, disease progression, death, lost to follow-up, subject's decision or consent withdrawn.
n	PK samples will be collected during Cycle 1 and Cycle 2 only. On Cycle 1 Day 1 postdose at 2 h (\pm 10 min) and 6 h (\pm 30 min). PK samples will be collected on Cycle 2 Day 1 predose (just prior to dosing) and postdose at 2 h (\pm 10 min). PK blood samples for encorafenib/binimetinib and potentially relevant metabolites will be processed to plasma. PK blood samples for cetuximab will be processed to serum.
o	Optional tumor sample will be requested only for subjects that discontinue study drug treatment due to disease progression.

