13. STATISTICAL ANALYSIS

13.1. GENERAL CONSIDERATIONS

A detailed statistical analysis plan (SAP) will be prepared by the Sponsor. This plan may modify the statistical methods outlined in the protocol; however, any major modifications related to the primary outcome measure definition or analysis will also be described in a protocol amendment.

The statistical analysis will be done under the supervision of the study statistician at the Biometry Department, IRPF. Analyses will be programmed in accordance with the SAP.

The CSR is planned to be written at the time of the primary outcome measure analysis (after Stage 1 if the study is stopped for futility, otherwise after Stage 2).

The cut-off date for futility analysis and Stage 2 analysis is estimated to occur approximately when all treated subjects with a centrally confirmed *BRAF*^{V600E} mutation of the concerned stage have either discontinued or have four post-baseline tumor assessments. And in case the last subject required for the concerned stage has an objective response, it should be confirmed in the following tumor assessment before the analysis is being performed. However, it will be possible to proceed to Stage 2 as soon as 40 subjects with a centrally confirmed *BRAF*^{V600E} mutation are treated and 12 confirmed responses are observed.

All available data will be included at the time of the cut-off date for secondary time-to-event endpoints and safety assessments. Unless the study is stopped at an earlier point in time, any further CSR update (or addendum) will be written at the end of study.

After the primary outcome measure analysis (after Stage 1 if the study is stopped for futility, otherwise after Stage 2), an analysis will be performed at the end of the Main study period, and at the end of the Study extension period).

Descriptive methods will be used to present all relevant data:

- Continuous data will be summarized with: frequency, median, range, mean, standard deviation and standard error if relevant.
- Categorical data will be presented in contingency tables with frequencies and percentages of each modality.

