#### 9.1.2. Dates and period

*Date of first administration of study treatment* is derived as the first date when a non-zero dose of any study drug was administered and recorded on the eCRF.

*Date of last administration of study treatment* is defined as the last date when a non-zero dose of any study drug was administered and recorded on the eCRF. Note: if at a given analysis time point, the patient has a start date but with no end date and no EOT page is filled-in, the patient will be

considered as ongoing and the end date will be imputed to the cut-off date for the calculation of treatment duration.

*Last contact date* will be derived for patients (known to have died or not) at the analysis cut-off. Imputed date (e.g. analysis cut-off date programmatically imputed to replace the missing end date of a dose administration record) will **not** be considered for the determination of last contact date. Only dates associated with patient visits or actual examinations of the patient will be used in the derivation. If after derivation, the last contact date is posterior to the cut-off date, then the last contact date will be taken to be the cut-off date. Last contact date will only be derived using the latest complete date among the following:

- Start/end date of study medication with non-missing dose (doses of 0 are allowed);
- RECIST assessment date with evaluation marked as “done”;
- Laboratory/PK collection date with sample collection marked as “done”;
- Vital sign date with non-missing parameter value;
- Cardiac evaluation date with non-missing parameter value;
- ECG evaluation date with non-missing parameter value;
- Ophthalmologic evaluation date with non-missing parameter value;
- Physical examination date with non-missing parameter value;
- Questionnaire evaluation date with non-missing parameter value;
- Performance status date with non-missing performance status;
- Start/end date of adverse events with non-missing/non-“None” verbatim term and outcome different from “Fatal” and grade less than 5
- Start date of fatal AE (i.e. outcome “Fatal” and grade 5) when the Start date is strictly before the end date
- Start/end date of antineoplastic therapies administered after study treatment discontinuation with non-missing medication/procedure term;
- Date of contact in survival status when the patient is marked as alive;

- Treatment assigned date.

*FPFV used for analysis* will be defined as the earliest date of first study treatment administration.

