### 14.1. PRIMARY ENDPOINT: CONFIRMED ORR BASED ON INVESTIGATOR-ASSESSED TUMOR EVALUATION

#### BOCR

The best overall confirmed response (BOCR) will be derived as per RECIST guideline version 1.1.

Only tumor assessments performed before the start of any further antineoplastic therapies (i.e. any additional secondary antineoplastic medication or anti-cancer surgery or radiotherapy) and not later than 30 days after last study treatment administration will be considered in the assessment of BOCR. Clinical deterioration or clinical progression noted on the end-of-treatment eCRF will not be considered as documented disease progression.

The BOCR for each subject is determined from the sequence of overall (lesion) responses according to the following rules:

- CR: at least two determinations of CR at least 4 weeks apart before progression
- PR: at least two determinations of PR or better at least 4 weeks apart before progression (and not qualifying for a CR)
- SD: at least one SD assessment (or better)  $\geq 6$  weeks after start of treatment (and not qualifying for CR or PR).
- PD: early progression  $\leq 9$  weeks after first study treatment administration (and not qualifying for CR, PR or SD).
- NE = all other cases (i.e. not qualifying for confirmed CR or PR and without SD  $\geq 6$  weeks or early progression  $\leq 9$  weeks after first study treatment administration)

Best overall confirmed response will be summarized, with reasons for having unknown status in Non-Evaluable patients, including:

- No baseline assessment, no measurable disease at baseline
- No post-baseline assessment
- All post-baseline assessments have overall response of “NE”
- New antineoplastic therapy (i.e. any additional secondary antineoplastic medication or anti-cancer surgery or radiotherapy) started before first post-baseline assessment
- Unconfirmed CR, PR or SD with first adequate assessment < 6 weeks Progression >9 weeks after first study treatment administration

The following table, based on Table 3 from the RECIST 1.1 guidelines, summarizes the algorithm describing how Best Overall Confirmed Response (BOCR) is determined from the overall tumor assessments. The order used to determine the BOCR is CR>PR>SD>PD, ignoring visits with missing tumor assessments.

All assessments following an assessment of PD will be excluded from the derivation of BOCR.

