#### 14.2.2. ORR (for confirmed+unconfirmed responses) based on investigator-assessed tumor evaluation

Objective Response Rate, considered for confirmed + unconfirmed responses as per local radiologist/investigator assessment, will be analyzed in the same manner as the primary analysis for the ES and FAS.

The best overall response (BOR) for confirmed + unconfirmed responses will be derived as per RECIST guideline version 1.1.

Only tumor assessments performed before the start of any further antineoplastic therapies (i.e. any additional secondary antineoplastic medication or anti-cancer surgery or radiotherapy) and not later than 30 days after last study treatment administration will be considered in the assessment of BOR. Clinical deterioration or clinical progression noted on the end-of-treatment eCRF will not be considered as documented disease progression.

The BOR for each subject is determined from the sequence of overall (lesion) responses according to the rules displayed in section 14.1.

- CR: at least one determination of CR before progression
- PR: at least one determination of PR before progression
- SD: at least one SD assessment (or better)  $\geq 6$  weeks after start of treatment (and not qualifying for CR or PR).
- PD: early progression  $\leq 9$  weeks after first study treatment administration (and not qualifying for CR, PR or SD).
- NE = all other cases (i.e. not qualifying for confirmed CR or PR and without SD  $\geq 6$  weeks or early progression  $\leq 9$  weeks after first study treatment administration)

Best overall response (confirmed+unconfirmed) will be summarized, with reasons for having unknown status in Non-Evaluable patients, including:

- No baseline assessment, no measurable disease at baseline

- No adequate post-baseline assessment
- All post-baseline assessments have overall response of “NE”
- New antineoplastic therapy (i.e. any additional secondary antineoplastic medication or anti-cancer surgery or radiotherapy) started before first post-baseline assessment
- SD occurred <6 weeks after first study treatment administration
- Progression >9 weeks after first study treatment administration

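### The SAP's 30-day limit on scans for best response can discard a required confirming scan when all three drugs stop soon after a first CR or PR, so that subject counts as a non-responder in cORR

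*Protocol*

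**What the plan says.** **Scans after stopping.** Footnote m of the protocol's main-period flow-chart covers subjects who stop for reasons other than progression: "tumor assessments must be performed (as per local and central review) every 6 weeks (first 12 weeks) then every 8 weeks", until progression, new anticancer therapy, death, loss to follow-up or withdrawal. Protocol 8.1 and 9.1.10 repeat this. The procedure lists for the end-of-treatment and 30-day visits (9.1.9, 9.1.10.1) contain no tumor scan.

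**Scans that count for response.** SAP 14.1 admits only scans before any further antineoplastic therapy and "not later than 30 days after last study treatment administration will be considered in the assessment of BOCR". SAP 14.2.2 has the same limit for confirmed plus unconfirmed response: "not later than 30 days after last study treatment administration will be considered in the assessment of BOR". Central-review BOCR is derived in the same way (SAP 14.2.1). In SAP 9.1.2 the date that starts the clock "is defined as the last date when a non-zero dose of any study drug was administered and recorded on the eCRF".

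**Confirmation.** SAP 14.1 requires, for PR, "PR: at least two determinations of PR or better at least 4 weeks apart before progression". The cORR denominator is the whole analysis set.

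**Timing of the analysis.** The protocol synopsis, protocol 13.15 and SAP 6.5 hold the stage 2 cut-off until subjects with an initial response have had the chance of a confirmation scan.

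**Elsewhere.** Protocol 13.2.1 defines cORR per RECIST 1.1 with no 30-day limit. The RECIST appendix (17.6.4) runs best response to the end of treatment, and adds that a protocol should make clear whether post-treatment scans count. SAP section 20 does not list the limit as a change.

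**The concern.** Both scheduled gaps between scans are longer than 30 days. A subject with a first CR or PR shortly before all treatment stops will therefore have the next scheduled scan outside the SAP window. The protocol requires that scan, and the cut-off is timed to allow for it, but the primary endpoint does not use it. If it still shows response, with no progression and no new therapy, the subject meets the four-week confirmation rule in substance but is not counted.

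The decision rules are exact counts: 12 of 40 to continue and 37 of 90 to reject. One uncounted responder can therefore decide either. The loss is not random either: it falls on responders who stop early without progression, for example for toxicity. The same subject is an event in the main TTR analysis, where response need not be confirmed, and stays in follow-up for PFS. The subject is absent from DOR, which is restricted to confirmed responders.

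**Working it through.** **1. The plan's own figures.** With p the true cORR, the probability of rejection is the sum over x = 12 to 40 of P(X₁ = x | n = 40) × P(X₂ ≥ 37 − x | n = 50). At p = 0.30 this gives 1.61% (stated 1.6%). At p = 0.45 it gives 79.8% (stated 80%). Both reproduce.

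**2. When the confirming scan is lost.** Let G be the days between the first-response scan and the next scan, and d the days from the first-response scan to the last dose. The next scan falls G − d days after the last dose, and is excluded if G − d > 30, that is, if d < G − 30. Nominal scan days are 42, 84, 140 and so on.

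| First response | G (days) | Excluded if d is below | G over visit windows | Range of the limit on d |
|---|---|---|---|---|
| Week 6 | 42 | 12 | 28–49 | 0–19 |
| Week 12 or later | 56 | 26 | 42–70 | 12–40 |

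The windows are ±7 days, except at the first scan: "The time window allowed for the first tumor assessment (i.e. day 42 from first dose) is +7 days".

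**3. Classification.** With no later countable scan, SAP Table 10 case 15 gives SD if the response scan was at least 42 days after first dose, and NE otherwise. Either way the subject is in the denominator and not in the numerator.

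**4. Size, under assumptions.** The documents give neither the timing of first responses nor the rate of stopping all drugs without progression. Assume a share f of first responses at week 6, from 0.5 to 0.7, and permanent non-progression discontinuation at rate h per 28 days, from 0.01 to 0.04. The share of responders lost is

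m = f × (1 − exp(−12h/28)) + (1 − f) × (1 − exp(−26h/28)).

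- h = 0.01, f = 0.7: 0.7 × 0.00428 + 0.3 × 0.00924 = 0.0058
- h = 0.04, f = 0.5: 0.5 × 0.01700 + 0.5 × 0.03646 = 0.0267

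Expected responders at 45% are 0.45 × 90 = 40.5, so the expected loss is 0.2 to 1.1 subjects. At these rates this is an upper bound for this route, because some of these subjects would progress or start new therapy before the confirming scan.

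**5. Effect on power, if 45% is the rate with all scans counted.** The counted rate is 0.45 × (1 − m). Putting it into the formula of step 1:

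| m | Counted rate | Power |
|---|---|---|
| 0 | 45.0% | 79.8% |
| 0.58% | 44.7% | 78.4% |
| 2.67% | 43.8% | 72.8% |
| 5% (stress case) | 42.75% | 65.8% |

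**6. Direction.** The limit only removes responses. At a true rate of 30%, a 1% loss lowers the rejection probability from 1.61% to 1.37%. Type I error is not inflated.

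**The case against.** **The protocol may allow the limit.** The RECIST appendix ends best response at the end of treatment. Read literally, last dose plus 30 days is more generous than that. This stands to the extent that it rules out a clean contradiction between protocol and SAP. But the appendix reproduces generic RECIST text, and that text itself asks each protocol to settle the matter, which this one does not do. The reader is left with three windows: none in 13.2.1, end of treatment in the appendix, and 30 days in the SAP.

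**Scans may be collected for other reasons.** Post-treatment scans are needed for PFS and DOR, so requiring them does not oblige anyone to use them for response. A pre-stated limit that can only lower cORR is a defensible convention in a single-arm trial. This also stands, and it is why complete removal of the limit is debatable. It does not explain holding the cut-off for a confirmation scan that the endpoint then excludes.

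**Stronger readings that do not hold.** A reader might infer that any responder who stops for toxicity becomes a non-responder. That is not so: two qualifying scans at least four weeks apart, both by day 30 after the last dose, are enough. Nor does stopping one drug start the clock, because it runs from the last dose of any of the three; protocol 6.5.4 lets subjects stop binimetinib and continue the other two. Nor does the SAP ignore late scans in general, since the PFS, DOR and TTR rules carry no 30-day limit. An on-treatment unconfirmed response also still counts in the secondary ORR.

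Finally, a reader might conclude that the stated 80% power is not delivered. The documents do not say that 45% assumes an unlimited scan window. If 45% is the rate under the SAP's definition, 79.8% is correct.

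**Conclusion.** The point holds for a specific group: subjects whose first CR or PR comes shortly before the last dose of all study drugs, and who still show response at the next scheduled scan without progression or new therapy. They are counted as non-responders in the primary endpoint and left out of DOR, although the confirming scan is required by protocol.

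The bias is downward only. It is probably small: at most about 0.6–2.7% of responders, or 0.2–1.1 of 40.5, under the assumed discontinuation rates and response timing. If 45% is taken as the rate with all scans counted, power is about 73–78% rather than 79.8%. No figure stated in the plan is wrong. The case for acting rests on the exact-count thresholds, the low cost, and the lack of a single stated window for the primary endpoint.

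**What to change.** 1. **SAP 14.1, with matching wording in 14.2.2.** Let a CR or PR first documented on treatment, or within 30 days of the last dose, be confirmed by the next protocol-scheduled scan, provided that scan precedes progression and any new antineoplastic therapy. In 14.2.2 this is for consistency only, because the first response already counts there.
2. **If the 30-day limit stays primary,** add a sensitivity cORR that uses all scans before progression or new therapy. This is the safer route if response data have been seen. The SAP's version history records an analysis added after the stage 1 Steering Committee, whose remit includes the response results, which suggests that they have.
3. **Both documents.** State the same window in protocol 13.2.1 and the RECIST appendix, and list it in SAP section 20. Protocol 13.1 says that "any major modifications related to the primary outcome measure definition or analysis will also be described in a protocol amendment". Whether this change is major is for the sponsor to judge and record.

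The cost is some wording and one extra table. The scans are already required, so no new data are needed. The drawback is that some confirming scans will have been taken off treatment, which the report should note.

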1. INTRODUCTION AND STUDY RATIONALE

1.1. BACKGROUND INFORMATION ON THE TARGET PATHOLOGY AND THERAPY

Metastatic colorectal cancer (mCRC) continues to be a serious, life-threatening condition. According to GLOBOCAN data, 1.36 million new cases affecting 17.2 individuals per 100000 population (746000 men and 614000 women) are diagnosed in the world each year, and 693000 people (373000 men and 320000 women) die from colorectal cancer (CRC), accounting for a yearly mortality rate of 8.4 per 100000. In the United States, the American Cancer Society's estimate for the number of colorectal cancer cases for 2017 are 95,520 new cases. In the World Health Organisation (WHO) European Region, CRC is the first tumor by incidence, with 471000 new cases each year and a mean mortality rate of 28.2 per 100000 population.

Approximately 25% of subjects present with metastases and 50% eventually develop metastatic disease (**Van Cutsem et al, 2014**).

Standard therapy in subjects with unresectable mCRC includes combination regimens with cytotoxic and targeted agents. In the last decade, substantial advances in the treatment of mCRC have resulted in an improvement in overall survival (OS) from 10 to 12 months to more than 20 months. This improvement is thanks to the addition of irinotecan, oxaliplatin, bevacizumab, cetuximab, and panitumumab to the standard treatment with 5-fluorouracil (5 FU)/folinic acid (FA).

BRAF^{V600E} MUTANT COLORECTAL CANCER

BRAF mutations, which lead to constitutive activation of BRAF kinase and sustained RAS/RAF/MEK/ERK pathway signaling resulting in increased cell proliferation and survival, occur in approximately 10% (range, 5–22%) of the unselected CRC population (**Rozek LS et al, 2010; Shaukat A et al, 2010**).

According to the European Society of Medical Oncology (ESMO) Consensus Guidelines for the management of subjects with mCRC (**Van Cutsem E et al, 2016**), *BRAF* mutation status should be assessed alongside *RAS* mutation status for prognostic assessment (and/or potential selection for clinical trials) [level I, B].

In the United States (US), the National Comprehensive Cancer Network panel (NCCN) strongly recommends genotyping of tumor tissue (either primary tumor or metastasis) in all subjects with mCRC, for *RAS* (KRAS exon 2 and non-exon 2; NRAS) and *BRAF* upon diagnosis of stage IV disease (**Benson AB et al, 2017**) Testing for the *BRAF*^{V600E} mutation (*BRAF*^{V600E}) can be performed on formalin-fixed paraffin-embedded (FFPE) tissues and is usually performed by polymerase chain reaction (PCR) amplification and direct Deoxyribonucleic Acid (DNA) sequence analysis.

The presence of a *BRAF*^{V600E} mutation is considered a marker of poor prognosis in subjects with mCRC and is associated (in the first line setting for metastatic disease) with a median survival of approximately 12 to 14 months compared to 21 to 25 months for subjects with *BRAF* wild-type (*BRAF*_{wt}) tumors (**Van Cutsem E et al, 2011**). Failure to achieve good survival outcomes through standard doublet chemotherapy agents in subjects with *BRAF*^{V600E} mutant mCRC has ignited efforts to combine multiple target therapies (**Kopetz S et al, 2017; Corcoran RB et al, 2016**).

First line treatment options for *BRAF*^{V600E} mutant mCRC patients

Currently, there are no agents specifically indicated for subjects with *BRAF*^{V600E} mutant mCRC. However, since *BRAF* and *KRAS* mutations are almost always mutually exclusive, subjects with *BRAF*^{V600E} mCRC have typically been treated with standard-of-care regimens for *RAS*_{wt} mCRC. Subjects with *RAS*_{wt} mCRC typically receive infusional 5-FU/FA/oxaliplatin (FOLFOX) or (5-FU/FA/irinotecan (FOLFIRI) with or without bevacizumab (anti VEGF antibody) or cetuximab (anti EGFR antibody) as initial therapy. A retrospective study reported no differences in PFS irrespective of whether oxaliplatin- or irinotecan-based chemotherapy was administered in the first-line setting in patients with *BRAF* mutant CRC (6.4 versus 5.4 months; P=0.99). (**Morris V et al, 2014**). There is insufficient evidence to conclude that *BRAF* is a predictive biomarker for irinotecan or oxaliplatin, as patients benefit regardless of their mutational status.

Some authors have proposed more intensive treatment based on the combination of 5-fluoruracil, leucovorin, oxaliplatin, irinotecan and bevacizumab (FOLFOXIRI-Beva) based on a retrospective analysis of a prospective phase II trial evaluating this combination, (Loupakis F et al, 2014) which included 15 *BRAF* mutant CRC patients. Results were initially encouraging compared with historical controls with median PFS and OS of 11.8 and 24.1 months and a 72% response rate (RR).

In the follow up phase III trial which randomized a total of 28 patients with *BRAF* mutant mCRC, FOLFOXIRI-Bev had improved results compared with FOLFIRI Bev with respect to OS (median 19.0 versus 10.7 months; HR, 0.84; 95% CI, 0.24–1.2), PFS (median 7.5 versus 5.5 months; HR, 0.57; 95% CI, 0.27– 1.23), and ORR (55% versus 42%; Odd Ratio, 1.82; 95% CI, 0.38–8.78).

Use of EGFRi with standard chemotherapy in the first line setting for *BRAF*^{V600E} mutant mCRC patients

Limited data from unplanned retrospective subset analyses of subjects with mCRC treated in the first-line setting suggest that, although a *BRAF*^{V600E} mutation confers a poor prognosis regardless of treatment, subjects with disease characterized by this mutation may receive some benefit from the addition of cetuximab to front-line therapy (Van Cutsem E et al, 2011; Bokemeyer C et al, 2012). On the other hand, results from the randomized phase III Medical Research Council (MRC) COIN trial suggest that cetuximab may have no effect or even a detrimental one in subjects with *BRAF*-mutated tumors treated with CapeOx (Douillard JY et al, 2013; Maughan TS et al, 2011).

While data suggest *BRAF* mutation status has clear prognostic value in mCRC, its predictive value for response and benefit from EGFR-directed treatments, such as cetuximab, remain controversial. Retrospective analyses of recent trials have suggested that *BRAF* mutations are not predictive of outcome with EGFR-directed therapies (Tol J and Punt CJ, 2010) in certain settings whereas other analyses have suggested that cetuximab and panitumumab are most active in subjects with *BRAF*wt mCRC (Di Nicolantonio F et al, 2008; De Roock W et al, 2010). In a recent meta-analysis of 7 randomized controlled trials in which subjects received panitumumab or cetuximab in different lines of therapy, and with a range of background chemotherapy, no significant interaction was noted between the benefits of anti-EGFR therapy (measured as OS and PFS) and the presence of *BRAF* mutations. These results suggest that anti-EGFR therapy may have benefit for subjects with

BRAF^{V600E} CRC. Consistent with this recent publication, a joint committee of the American Society for Clinical Pathology (ASCP), the College of American Pathologists (CAP), the Association for Molecular Pathology (AMP), and the American Society of Clinical Oncology (ASCO), issued draft guidelines for the evaluation of molecular markers for CRC which stated that there is insufficient evidence to recommend *BRAF*^{V600E} mutation status as a predictive molecular marker for response to EGFR directed therapies (see **Table 1**).

Table 1: First line Phase II and III clinical trials with EGFR and VEGFi and *BRAF* mutational status for metastatic colorectal cancer subjects

Reference	No of patients	Treatment	BRAFm (%)	OS (months)	PFS (months)	RR
NORDIC (Tveit KM et al, 2012)	457	FLOX+C FLOX	20	NA	NA	19.4% 21% NSS
CRYSTAL/OPUS (Bokemeyer C et al, 2012)	1535	FOLFIRI/FOLFOX+C FOLFIRI/FOLFOX	8.2	14.1 9.9 HR, 0.62 P=0.076	7.1 3.7 HR, 0.67 P=0.23	21.3% 13.2% OR,1.6 P=0.46
COIN (Smith CG et al, 2013)	2445	FP + Oxaliplatin + C FP + Oxaliplatin	9	7.2 10 HR 1.18 P=0.46	NA NA HR1.25 P=0.54	NA
PRIME (Douillard JY et al, 2013)	1183	FOLFOX + P FOLFOX	10	10.5 9.2 HR0.9 P=0.76	6.1 5.4 HR0.58 P=0.12	NA
FIRE 3 (Stintzing S et al, 2014)	342	FOLFIRI + C FOLFIRI + Bev	13.7	12.3 13.7 HR0.87 P=0.65	4.9 6 HR0.87 P=0.64	52.2% 40% OR 1.64 P=0.29
TRIBE (Cremolini C et al, 2015)	508	FOLFIRI + Bev FOLFOXIRI+Bev	5.5	10.7 19.0 HR:0.54	5.5 7.5 HR=0.57	42% 56% OR:1.82 (0.38-8.78)

Treatment options after first line for *BRAF*^{V600E} mutant mCRC patients

In a retrospective analysis of subjects with chemo-refractory mCRC treated with chemotherapy and an anti-epidermal growth factor receptor (EGFR) agent, the median progression-free survival (PFS) and OS in subjects with *BRAF* mutant tumors were 2 months and 6.5 months, respectively, compared with a median PFS of 6.5 months and a median OS of 13.5 months in subjects with *BRAF*wt tumors. In a study evaluating 5-FU/FA/irinotecan (FOLFIRI) plus panitumumab in a pure second-line setting, subjects with *BRAF*^{V600E} mutant mCRC had a median PFS of 2.5 months and a median OS of 4.7 months, compared with a median PFS and a median OS of 6.9 and 18.7 months, respectively, in subjects with *BRAF*wt tumors. Finally, in 71 subjects with *BRAF*^{V600E} mutant mCRC treated at the MD Anderson Cancer Center between 2003 and 2012, the median PFS with second-line therapy was 10 weeks in the overall group (n=58) and 12 weeks in subjects who were treated with an irinotecan-based regimen (n=39), 28 of whom had received panitumumab or cetuximab concomitantly with irinotecan. The median PFS in subjects receiving second- or third-line therapy corresponded to the timing of the first restaging scan (Morris V et al, 2014).

Benefits of combination therapies have been demonstrated in clinical studies of patients with mCRC, including: dual inhibition of BRAF + EGFR such as panitumumab + dabrafenib (Corcoran RB et al, 2016) and cetuximab + encorafenib (Tabernero J et al, 2016), the ORR reported in these studies were 10% and 22%, respectively; or triplet combinations consisting of BRAF + EGFR inhibition plus MEK inhibition or chemotherapy such as cetuximab + vemurafenib + irinotecan (Kopetz S et al, 2017) or panitumumab + dabrafenib + trametinib (Corcoran RB et al, 2016), the ORR reported in these studies were 16% and 21% respectively. In particular, the phase II study of cetuximab + encorafenib demonstrated a median PFS of 4.2 months, and the median overall survival exceeded 1 year, which is substantially improved over the historical standard of care for this population.

Inhibition of BRAF, MEK, and EGFR in *BRAF*^{V600E} Colorectal Cancer Cells

Cancer cells with *BRAF* mutations are highly dependent on MEK/ERK signaling. As demonstrated in melanoma cells, MEK-dependent activation of MAP Kinase (MAPK) signaling occurs following BRAF inhibition and near-complete inhibition of phospho-ERK is required for tumor responses.

The combination of a BRAF inhibitor and a MEK inhibitor has been shown to be more active than either agent alone, presumably due to delaying or preventing resistance (**Thakur MD and Stuart DD, 2014**). Nonclinical studies in CRC cells has shown that BRAF inhibition causes a rapid feedback activation of EGFR that supports continued proliferation of *BRAF*^{V600E} CRC tumor cells (**Corcoran RB et al, 2012; Prahallad A et al, 2012**). Activation of EGFR can be effectively prevented by the combination of vemurafenib with anti-EGFR agents such as the small-molecule kinase inhibitor, erlotinib, or the monoclonal antibody, cetuximab.

These reports suggest that activation of EGFR may partially explain the limited therapeutic effect of *BRAF* inhibitor monotherapy in subjects with *BRAF*^{V600E} mutant mCRC and that this can be overcome with concomitant EGFR inhibition. The dependence of *BRAF*-mutant CRC cells on MAPK signaling provides a compelling rationale for inhibiting MEK in addition to *BRAF* and EGFR to achieve more robust inhibition of the pathway.

